### 6.2. Screen Failures

Screen Failures will not be summarized.

### **6.3. Protocol Deviations**

All protocol deviations are listed. Protocol deviations may include excluded medications, patients entering the study despite not satisfying all entry criteria, patients receiving wrong treatment or incorrect dose, or other major protocol deviations.

### **6.4. Demographic and Baseline Characteristics**

Summaries of demographic and other baseline characteristic data are presented by treatment group for all analysis populations. They may also be summarized by select subgroup as appropriate.

The demographic and other baseline characteristics include:

- Baseline Age
- Sex, Race, Ethnicity
- Weight (kg), Height (cm), BMI (kg/m^2)
- Diastolic and systolic blood pressure (mmHg), Heart rate (bpm)
- Serum creatinine
- eGFR, eGFR categorical status ([Table 5](#)), (< 30; 30-<45; >=45), (<45; >=45)
- UACR, UACR categorical status (≤ 300; > 300)
- Prognosis of CKD by eGFR and Albuminuria categories (low, moderate, high, very high)
- KDIGO Stratification: CKD progression risk heat map: yellow/orange; red/dark red
- Angiotensin converting enzyme (ACE)-inhibitor treatment and/or Angiotensin II receptor blocker (ARB) (yes/no)
- Kidney Etiologies (Diabetes, Hypertension, and Other.)
- Family History of CKD
- Other baseline variables of interest

### **6.5. Listing of Subject Inclusion and Exclusion Criteria**

A listing of enrolled patients who did not meet inclusion or exclusion criteria is generated.

### **6.6. Medical History**

Medical history is summarized by treatment. Medical history is coded using MedDRA (Medical Dictionary for Regulatory Activities) version 21.1. Medical history items are summarized by MedDRA SOC and PT. A by-patient listing of medical history will be provided.

## 7. PRIMARY EFFICACY

Analyses of efficacy described in this section are the primary analyses of the efficacy endpoints, and pertain to the ITT population (i.e., all patients randomized in the study), unless otherwise specified. The trial includes endpoints at 12 weeks on-treatment and 5 weeks off-treatment. Additional details regarding the statistical approach and pseudo SAS code are available in the programming conventions document.

The following abbreviations are used in descriptions of the ANCOVA and MMRM analysis models:

**Table 7: Model Parameter Abbreviations**

Abbreviation	Model Term
HEAT_STRAT	KDIGO heat map stratification (stratum 1 and 2)
TRT	treatment group
VISIT	analysis visit used as time
TRT x VISIT	the interaction between treatment and time

### 7.1. General Considerations

Results will not be presented by individual study centers. Analyses are performed for all bardoxolone methyl patients in comparison with all placebo patients. Summary statistics for observed values, change from baseline, and percent change from baseline are presented by randomized treatment group. Missing values are handled as described in Section 5.6.

### 7.2. Statement of the Null and Alternate Hypothesis

The primary efficacy analysis compares the change from baseline in eGFR for patients randomized to bardoxolone methyl ( $\mu$  BARD) to the change from baseline in eGFR for patients randomized to placebo ( $\mu$  placebo) at the endpoint-specified visit according to the following hypotheses:

- Null hypothesis,  $H_0: (\mu \text{ BARD}) - (\mu \text{ placebo}) = 0 \text{ mL/min/1.73 m}^2$
- Alternative hypothesis,  $H_1: (\mu \text{ BARD}) - (\mu \text{ placebo}) \neq 0 \text{ mL/min/1.73 m}^2$

Because eGFR decreases with disease progression, an increase in eGFR relative to placebo is considered evidence of benefit.

### 7.3. Subgroup Analysis

The off-treatment efficacy endpoints, the primary efficacy endpoint and secondary efficacy endpoint, will be descriptively analyzed for subgroups of interest to assess the general consistency of results across subgroups.

The following subgroup analyses are tabulated:

- Sex: female; male
- Ethnicity: Non-Hispanic/Latino; Hispanic/Latino
- Race: White; Non-White
- Baseline BMI ( $\text{kg}/\text{m}^2$ ):  $< 30$ ;  $\geq 30$
- Baseline eGFR ( $\text{mL}/\text{min}/1.73 \text{ m}^2$ ):  $< 30$ ;  $30-45$ ;  $\geq 45$
- Baseline eGFR ( $\text{mL}/\text{min}/1.73 \text{ m}^2$ ):  $< 45$ ;  $\geq 45$
- Baseline UACR ( $\text{mg}/\text{g}$ ):  $\leq 300$ ;  $> 300$
- Family history of CKD: Yes; No
- Kidney Etiologies (Diabetes, Hypertension, and Other)
- KDIGO Stratification: CKD progression risk heat map: yellow/orange; red/dark red
- Patients with IP Interruptions (Yes/No)

Subgroup analyses will include nominal significance levels for descriptive purposes only. The model used for subgroup analyses is the same as the primary analyses (Section 7) with additional terms of subgroup and subgroup-by-treatment.

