#### 9.1.1. Management of Fluid Status

Specific risk mitigations procedures will be employed to reduce the potential for bardoxolone methyl-induced fluid overload. These procedures include exclusion of patients with any severe kidney disease, defined as an eGFR value of  $< 20 \text{ mL/min/1.73 m}^2$ . To exclude patients with significant cardiac dysfunction, the study will exclude patients with a history of clinically significant cardiac disease. Patients who have evidence of volume overload at baseline, defined as BNP level of  $> 200 \text{ pg/mL}$ , will also be excluded.

Laboratory data and rapid weight gain will also be used to monitor fluid status after randomization. Patients who experience a BNP  $> 100 \text{ pg/mL}$  that represents a doubling (or more) of BNP levels from Day 1 should have an unscheduled telephone contact immediately (see Section 9.10.15 for description of telephone contact). In addition, patients will be given a Sponsor-provided scale to use at home to collect and record their weights daily during the first 8 weeks of the treatment period and weekly thereafter. Patients who experience a five-pound (2.3 kilograms) or greater increase in weight since their Day 1 weight during the first 8 weeks must have an unscheduled telephone contact immediately. Whether due to BNP elevations or weight gain, if clinically important fluid retention is suspected, the patient must be instructed to stop taking their study medication immediately and be medically evaluated by the investigator or a local physician within 1 to 2 days.

Investigators are encouraged to consider starting or increasing doses of diuretics (thiazides, loop diuretics) early after recognition of edema. This can be done concurrently with temporary drug discontinuation and re-initiation. Patients may not restart their study medication until the investigator has completed and documented an assessment of fluid overload.

Beyond Week 8, patients who experience a weight increase of five pounds (2.3 kilograms) or greater compared to Day 1 will be instructed to contact the clinic to assess the need for an unscheduled physical examination and laboratory assessment by the investigator. Study medication should not be discontinued unless clinically important fluid retention is suspected. If suspected, the patient must be instructed to stop taking their study medication immediately and be medically evaluated by the investigator or a local physician within 1 to 2 days.

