## 12. STATISTICS

### 12.1. Sample Size

With 70 patients enrolled (35 in each group), the study will have approximately 80% power to detect a difference between the two treatment groups in change from baseline in eGFR of 5.9 mL/min/1.73 m^2 for the primary endpoint at Week 12. The power calculation, which was based on a two-sided two-sample t-test, assumes the following:

- Two-sided Type I error rate of 0.05;
- Standard deviation of change from baseline in eGFR of 8 mL/min/1.73 m^2;
- A change from baseline in eGFR of approximately 5.9 mL/min/1.73 m^2;
- 15% drop-out and missing data will not be imputed.

Analysis of the primary endpoint will be based on the intent-to-treat (ITT) population and analyzed using mixed-model repeated measures (MMRM) with an unstructured covariance structure. The analysis method is expected to have at least as much power as the two-sample t-test used for study planning. Appropriate sensitivity analyses of the primary analysis will be specified in the Statistical Analysis Plan (SAP). The secondary efficacy endpoint will be tested for sufficiently large subgroups, but the study is not powered to show efficacy in the secondary efficacy endpoint.

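### The IP-interruption subgroup in SAP 7.3 is defined after randomization, so its between-arm comparison can be biased even when the drug has no effect on eGFR

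*SAP*

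**What the plan says.** SAP 7.3 names the off-treatment, primary and secondary efficacy endpoints and says they "will be descriptively analyzed for subgroups of interest to assess the general consistency of results across subgroups". The list that follows is sex, ethnicity, race, baseline BMI, two groupings of baseline eGFR, baseline UACR, family history of CKD, etiology, KDIGO stratum and, last, "Patients with IP Interruptions (Yes/No". Every item but the last is a demographic or baseline factor.

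The model for every item is the primary model "with additional terms of subgroup and subgroup-by-treatment". The section adds that "Subgroup analyses will include nominal significance levels for descriptive purposes only". It does not mark interruption as a post-randomization factor. The SAP does not say what counts as an interruption: no minimum length, no time window, and no rule on whether permanent discontinuation is included.

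Protocol 9.1.1 says that if clinically important fluid retention is suspected, "the patient must be instructed to stop taking their study medication immediately", and it provides for temporary discontinuation and restart. Protocol 9.10.8 repeats the stop instruction for weight gain in the first 8 weeks. Protocol 9.9 lets the investigator interrupt treatment for serious toxicity. Protocol 5.1.2.1 reports that the drug was associated with more fluid overload and heart failure hospitalization in an earlier Phase 3 trial.

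**The concern.** Randomization makes the arms comparable as a whole and within strata fixed before treatment. It gives no such protection within strata formed by what happens on treatment. If the drug brings on some interruptions that placebo would not, the active patients in the interrupted stratum were selected differently from the placebo patients in it, and the same holds for the non-interrupted stratum. If that selection also tracks eGFR outcome, a between-arm difference appears in each stratum that is not a treatment effect.

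The documents make both conditions plausible. Fluid retention leads to stopping the drug, and the drug has raised that risk before. Protocol 5.1.2.1 also says the drug probably promotes fluid retention in patients with more advanced renal dysfunction, so the trigger may follow renal status. The SAP 7.4.1 model adjusts for renal status only through the two-level KDIGO stratum.

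At stake is how one subgroup row is read. The table exists to judge consistency of effect. In this row an inconsistency may be selection, and an apparent consistency may hide a real difference.

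**Working it through.** **1. Scale, from the plan.** Protocol 12.1 gives 35 patients per arm, SD 8, 15% drop-out, "Two-sided Type I error rate of 0.05" and "A change from baseline in eGFR of approximately 5.9 mL/min/1.73", and states that "the study will have approximately 80% power to detect a difference between the two treatment groups". Evaluable patients are 35 × 0.85 = 29.75 per arm. A two-sample t-test has power 0.799 at 29.75 per arm and 0.802 at 30, so the plan's figure reproduces. SD 8 and the difference of 5.9 are the yardsticks below.

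**2. Model for the illustration.** The true eGFR effect is set to zero in everyone. A latent score, with correlation ρ to eGFR change, decides who interrupts: patients heading for a worse change are more likely to, and the drug lowers the threshold. With p the interruption rate, φ the standard normal density and z the (1 − p) quantile, the mean standardized score is −φ(z)/p among interrupters and +φ(z)/(1 − p) among the others. Stratum bias is ρ × 8 × (active mean − placebo mean).

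The rates and ρ are assumptions; neither document gives them.

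**3. Assumed 25% active, 10% placebo.**

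| Stratum | Active mean | Placebo mean | Difference | ρ = 0.3 | ρ = 0.5 |
|---|---|---|---|---|---|
| Interrupted | −1.271 | −1.755 | +0.484 | 0.3 × 8 × 0.484 = +1.16 | 0.5 × 8 × 0.484 = +1.94 |
| Not interrupted | +0.424 | +0.195 | +0.229 | +0.55 | +0.91 |

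The largest value is 1.94/5.9 = 33% of the planning difference. The false interaction is the gap between the rows: 1.16 − 0.55 = 0.61, up to 1.94 − 0.91 = 1.03. Bias is proportional to ρ, so reversing its sign reverses every entry.

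**4. Range, including cases with no bias.** Bias comes from the same formula. Rejection rates at the nominal 5% level come from 6,000 simulated trials per row, 35 per arm, one time point, with treatment, subgroup and their interaction in the model.

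| Interrupting, active vs placebo | ρ, active / placebo | Bias, interrupted | Bias, not interrupted | Rejection, interrupted / not | Interaction rejection |
|---|---|---|---|---|---|
| 20% vs 20% | 0.5 / 0.5 | 0 | 0 | 4.5% / 5.0% | 4.6% |
| 30% vs 10% | 0 / 0 | 0 | 0 | 5.1% / 5.4% | 5.2% |
| 30% vs 10% | 0.3 / 0.3 | +1.43 | +0.72 | 5.6% / 6.2% | 4.8% |
| 30% vs 10% | 0.5 / 0.5 | +2.38 | +1.21 | 6.3% / 9.2% | 4.6% |
| 40% vs 10% | 0.5 / 0.5 | +3.16 | +1.80 | 9.3% / 12.8% | 4.7% |
| 20% vs 20% | 0.5 / 0 | −5.60 | +1.40 | 25.0% / 10.5% | 29.8% |

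The first two rows show that bias disappears when either condition fails. The last row shows that equal rates are no safeguard if the reasons for interrupting differ by arm, and that the spurious effect can be harmful. The overall unstratified test rejected 4.7% to 5.4% of the time in these scenarios.

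**5. Precision.** At 25% and 10% of 35, the interrupted stratum holds 8.75 active and 3.5 placebo patients on average. The standard error is 8 × √(1/8.75 + 1/3.5) = 5.06, so a 95% interval is about ±10.

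**The case against.** The strongest reply is that little hangs on this row. SAP 7.3 calls the analyses descriptive and the significance levels nominal, no decision uses them, and the primary analysis in SAP 7.4.1 uses eGFR values whether or not the patient is on drug. All of that stands, and it caps the importance of the point. It does not cure the defect: a descriptive label limits the strength of a claim but does not make non-comparable groups comparable.

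A second reply is that noise swamps the bias. With a standard error near 5, a bias of 1.2 to 1.9 is under 0.4 standard errors, and in most scenarios the excess of false positives is modest. That is fair for the common-correlation cases. It fails when the reasons for interruption differ by arm, and an estimate that imprecise is itself a poor basis for judging consistency.

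A third reply is that many interruptions have causes the documents do not tie to the drug: necessary CYP3A4 inhibitors or inducers (Protocol 9.3.1), suspected pregnancy (Protocol 9.8.3), and COVID-19 site mandates, patient choice or supply (SAP 11.1). These would dilute the mechanism, by an unknown amount.

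A reader might also count aminotransferase rises and nausea among the interruption triggers. The protocol does not support that as a stated rule. Section 9.1.2 describes slower titration, repeat testing or permanent discontinuation, and 9.1.8 describes de-escalation. A BNP rise alone prompts a telephone contact (9.1.1). The documented drug-related routes are suspected fluid retention and serious toxicity, and they are enough.

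**Conclusion.** The point holds as a possibility of bias. Interruption is the only post-randomization item on the SAP 7.3 list, and the protocol gives concrete reasons why treatment may influence it. Its within-stratum comparisons and interaction can mislead even if the drug does nothing to eGFR.

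A reader might go further and infer that the comparison must be biased, even for a wholly inert drug. The documents do not support that. If treatment changes neither the rate of interruption nor its reasons, or if interruption is unrelated to eGFR outcome, the bias is zero.

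The figures of +1.2 to +1.9 and +0.5 to +0.9 mL/min/1.73 m² are illustrations on assumed rates and correlations, not estimates for this trial; size and direction cannot be fixed from the documents. The sample size, power and primary ITT result are untouched. This is a minor but clear correction.

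**What to change.** Remove IP interruption from the treatment-by-subgroup list in SAP 7.3. Define an interruption in the SAP: minimum length, time window, and whether permanent discontinuation counts. Report its frequency, reasons and the eGFR course of interrupters and non-interrupters within each arm, labelled as post-randomization, with no between-arm p-value or interaction test.

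The cost is one deleted bullet and a short definition. Temporary discontinuations and their reasons are already recorded (Protocol 8.3.1), and SAP 9.2 already has exposure summaries where the counts and reasons can sit. No new data are needed. What is lost is one exploratory between-arm row.

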## 7.3. Treatment Assignment and Rationale

Qualified patients will be randomized 1:1 to receive either bardoxolone methyl or placebo once daily throughout a 12-week dosing period. Randomization will be stratified using the KDIGO CKD progression risk heat map (stratum 1 = yellow or orange; stratum 2 = red or dark red) based on screening eGFR and UACR using RTSM.

A dose-titration regimen is being utilized to allow for individual dose optimization based on tolerability and based on the anticipated maximally efficacious dose of bardoxolone methyl, which may vary based on a patient's proteinuria status at baseline. Based on results from prior trials in patients with T2D and CKD, Reata has concluded that higher bardoxolone methyl doses may be required to have an optimal effect on eGFR following drug withdrawal in patients with macroalbuminuria. Specifically, eGFR improvements in patients with normo- or microalbuminuria were observed with a 20 mg bardoxolone methyl dose. In patients with macroalbuminuria, a 30-mg dose was required to produce a response that was similar to the patients with microalbuminuria treated at 20 mg. Consequently, the study includes dose titration up to a maximum dose of 20 mg for patients with  $UACR \leq 300 \text{ mg/g}$  and a maximum dose of 30 mg for patients with  $UACR > 300 \text{ mg/g}$ , as described in Section 7.4.1. From a safety perspective, the 30 mg dose may be associated with an increased incidence of nausea; however, the nausea experienced in previous trials is generally mild, transient, and clinically manageable.

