## **7.4. Dose Adjustment Criteria**

### **7.4.1. Dose Escalation**

Patients will receive either bardoxolone methyl or placebo once daily (preferably in the morning) throughout the study. Patients randomized to bardoxolone methyl will start with once-daily dosing at 5 mg and will dose-escalate to 10 mg at Week 2, to 20 mg at Week 4, and then to 30 mg (only if baseline UACR > 300 mg/g) at Week 6 unless contraindicated clinically, which should be discussed with the medical monitor. Patients randomized to placebo will remain on placebo throughout the study and will follow the same titration to maintain the blind. Dose escalation may need to proceed more slowly if the patient experiences early elevations in ALT/AST over ULN, e.g. at Week 2 (see Section 9.1.2). The dosing objective is to titrate patients to the maximum target dose determined by baseline UACR and maintain the maximum dose after initial dose-titration.

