The assessment of eGFR during the off-treatment (OT) period is used to assess bardoxolone methyl's effect on the irreversible loss of kidney function as well as any disease modifying effects. Available clinical pharmacodynamic and pharmacokinetic data with bardoxolone methyl suggest that acute effects on eGFR are expected to resolve within 10 to 14 days after stopping treatment. In the present study, eGFR will be assessed at multiple intervals during the OT period to characterize the timecourse of the washout of bardoxolone methyl's acute pharmacodynamic effects.

Patients with CKD with rapid progression or at risk of rapid progression are defined as those with a sustained decline in eGFR of more than 4 to 5 mL/min/1.73 m^2 per year ([KDIGO, 2013](#)). The collective clinical and nonclinical data suggest that bardoxolone methyl may be effective at ameliorating the rate of decline in eGFR in this patient population. Furthermore, increases in eGFR observed after 12 weeks of treatment may translate to a sustained eGFR response. In patients with CKD at risk of rapid progression, the potential impact of a sustained eGFR increase with bardoxolone methyl treatment may be clinically meaningful and could translate to a delay in progression to end stage kidney disease (ESKD).

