## 7.4. Primary Efficacy Endpoint

### 7.4.1. Primary Analysis of the Primary Endpoint

The primary endpoint of this study is the change in eGFR at Week 12. The change from baseline eGFR for patients treated with bardoxolone methyl is compared with placebo at Week 12 using mixed models repeated measures (MMRM) analysis with the following fixed factors: KDIGO strata (HEAT\_STRAT), treatment group (TRT), time (i.e., VISIT; analysis visit number), and the interaction between treatment and time (TRT x VISIT).

The trial design separates discontinuation of study drug from discontinuation of study follow-up. Therefore, patients may discontinue early from study drug while continuing follow-up with study visits and assessments. The primary analysis of eGFR at Week 12 uses available eGFR values irrespective of whether a patient is receiving treatment. The MMRM analysis uses all eGFR values collected through Week 12 according to analysis visits 1,2,4,6,8, and 12 (Section 5.3.3). An unstructured covariance matrix is used.

In the event the MMRM model with an unstructured covariance structure does not converge, the following covariance structures are substituted, in the order listed. Each subsequent covariance structure is used only if each previous covariance structure is used and no previous model converged.

1. Heterogeneous Toeplitz covariance structure (assuming different variances at each time point and that measurements taken closer together in time are more highly correlated than those taken farther apart).

2. Toeplitz covariance structure (assuming measurements taken closer together in time are more highly correlated than those taken farther apart).
3. First order auto-regressive [AR(1)] covariance structure (assuming measurements taken closer together in time are more highly correlated than those taken farther apart, but the correlation is more constrained than the Toeplitz structure).
4. Compound symmetry covariance structure (assuming equal correlation for measurements from a patient, regardless of how far apart in time they were taken). A compound symmetry covariance structure was assumed in the sample size calculation.

If the MMRM model does not converge using any of the aforementioned covariance structures, variables from the model statement may be removed.

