#### **7.4.1.1. Sensitivity Analysis of the Primary Endpoint – No Imputation for Missing Data**

The change from baseline eGFR for patients treated with bardoxolone methyl is compared with placebo at Week 12 using ANCOVA analysis with the following fixed factors: KDIGO strata (HEAT\_STRAT) and treatment group (TRT).

The ANCOVA analysis uses eGFR values collected in the Week 12 analysis window (Table 3). Missing Week 12 eGFR data are not imputed.

The difference between bardoxolone methyl and placebo in change from baseline of eGFR is estimated along with the 95% confidence interval at Week 12.

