### 8.1. Exploratory Efficacy Endpoint

#### 8.1.1. Off-Treatment MMRM eGFR Analysis

The exploratory endpoint of this study is the change in eGFR at Day 3, 7, 14, 21, 28, and 35 during the Off-Treatment portion of the study. The change from baseline eGFR for patients treated with bardoxolone methyl is compared with placebo at Day 3, 7, 14, 21, 28, and 35 using mixed models repeated measures (MMRM) analysis with the following fixed factors: KDIGO strata (HEAT\_STRAT), treatment group (TRT), time (i.e., VISIT; analysis visit number), and the interaction between treatment and time (TRT x VISIT).

The MMRM analysis uses all eGFR values collected from Week 12 to Week 17 according to off-treatment analysis visits 3,7,14,21,28, and 35 (Section [5.5.3.1](#)). An unstructured covariance matrix is used. Baseline value is original On-Treatment baseline value.

1. In the event the MMRM model with an unstructured covariance structure does not converge, the covariance structures are substituted as defined in Section [7.4.1](#).

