##### 8.1.1.1. Sensitivity Analysis of Off-Treatment eGFR analysis – No Imputation for Missing Data

The change from baseline eGFR for patients treated with bardoxolone methyl is compared with placebo using ANCOVA analysis with the following fixed factors: KDIGO strata (HEAT\_STRAT) and treatment group (TRT).

The ANCOVA analysis uses eGFR values collected in each off-treatment visit (3,7,14,21,28, and 35) analysis window ([Table 4](#)). Missing eGFR data per visit are not imputed.

The difference between bardoxolone methyl and placebo in change from baseline of eGFR is estimated along with the 95% confidence interval at each off-treatment visit (3,7,14,21,28, and 35).

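### SAP 7.3 adds no visit terms for subgroup to the six-visit MMRM, so Week 12 subgroup effects assume a subgroup difference that is the same at every visit

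*SAP*

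**What the plan says.** - **Subgroup model (SAP 7.3).** "The model used for subgroup analyses is the same as the primary analyses (Section 7) with additional terms of subgroup and subgroup-by-treatment". The section covers the primary, secondary and off-treatment efficacy endpoints. Its purpose is to show whether results are broadly consistent across subgroups. P-values are nominal and descriptive. Baseline UACR (300 mg/g or less against more than 300 mg/g) is one of the listed subgroups.
- **Primary model (SAP 7.4.1).** The fixed effects are HEAT_STRAT, TRT, VISIT and TRT x VISIT, with an unstructured covariance. "The MMRM analysis uses all eGFR values collected through Week 12 according to analysis visits 1,2,4,6,8, and 12".
- **Off-treatment model (SAP 8.1.1).** An MMRM of the same form that "uses all eGFR values collected from Week 12 to Week 17 according to off-treatment analysis visits".
- **Visit-specific ANCOVAs already in the SAP.** In 7.4.1.1: "The ANCOVA analysis uses eGFR values collected in the Week 12 analysis window". In 8.1.1.1: "The ANCOVA analysis uses eGFR values collected in each off-treatment visit (3,7,14,21,28, and 35) analysis window".
- **Titration (Protocol 7.4.1).** Active-arm patients start with "once-daily dosing at 5 mg and will dose-escalate to 10 mg at Week 2, to 20 mg at Week 4". A further step to 30 mg at Week 6 applies only when baseline UACR exceeds 300 mg/g.
- **Other detail.** SAP 7 refers to a programming conventions document for model details and pseudo-code. It is not among the documents reviewed.

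**The concern.** The primary model contains TRT x VISIT because its estimand belongs to one visit. The subgroup estimand also belongs to one visit, yet 7.3 adds only SUBGROUP and SUBGROUP x TRT. The overall treatment effect may still vary by visit. What is held constant is the subgroup main effect and the subgroup difference in treatment effect. SAP 7.3 does not state that assumption.

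A changing difference is plausible here. The planned dose before each visit is 5 mg at Weeks 1 and 2, 10 mg at Week 4, 20 mg at Week 6, and 20 or 30 mg at Weeks 8 and 12. A subgroup difference that scales with dose would be smaller early than at Week 12. For the two UACR groups the planned doses diverge only from Week 6, so only the Week 8 and Week 12 visits follow the divergence.

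At stake is what the tables are for. A constant term can understate a real Week 12 difference, or show one that has already closed.

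**Working it through.** **Inputs from the documents.** Protocol 12.1 gives 35 patients per arm, SD of change 8, difference 5.9, two-sided 0.05 and 15% drop-out. The SAP gives six visits.

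**The plan's own figure.** 35 x 0.85 = 29.75, about 30 per arm. The noncentrality is 5.9 / (8 x √(2/30)) = 2.86, and the two-sample t-test power is 80.2% (79.9% at 29.75). The stated 80% reproduces. The point does not rest on it, but it gives the setting below: 60 completers, SD 8 at Week 12.

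**Assumed, because the documents give no more.** Two equal subgroups; complete data; correlation exchangeable 0.4 or 0.7, or AR(1) 0.4, 0.7 or 0.8; SD either 8 at every visit or rising in equal steps from 4 (Week 1) to 8 (Week 12). The time patterns are also assumed.

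**Formula.** Let d be the true subgroup difference in treatment effect by visit and S the covariance. With TRT x VISIT in the model, the constant SUBGROUP x TRT term estimates w'd, where w = S⁻¹1 / (1'S⁻¹1). The bias of the Week 12 difference is w'd - d(Week 12). Each of two equal subgroups takes half, with opposite signs.

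**Example.** With equal SDs and exchangeable correlation, every weight is 1/6. For a Week 12 gap of 4:
- proportional to dose, 20 mg schedule: (1 + 1 + 2 + 4 + 4 + 4)/6 = 2.67
- proportional to dose, 30 mg schedule: (0.67 + 0.67 + 1.33 + 2.67 + 4 + 4)/6 = 2.22
- present only at Weeks 8 and 12: (4 + 4)/6 = 1.33

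**Range over the five correlations.**

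| Pattern of the difference | True at Week 12 | Reported, equal SDs | Reported, SD 4 to 8 |
|---|---|---|---|
| Proportional to dose, 20 mg schedule | 4 | 2.57 to 2.67 | -0.15 to 1.91 |
| Proportional to dose, 30 mg schedule | 4 | 2.22 to 2.29 | -0.58 to 1.50 |
| Weeks 8 and 12 only | 4 | 1.33 to 1.71 | -1.45 to 0.68 |
| 4 at Weeks 1-6, then closed | 0 | 2.29 to 2.67 | 3.32 to 5.45 |
| Constant | 4 | 4.00 | 4.00 |

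The last row shows that there is no bias when the assumption holds. With rising SDs the precise early visits dominate. At exchangeable 0.7 the weights are 0.92, 0.39, 0.11, -0.05, -0.15 and -0.21, so Week 12 itself enters with a negative sign.

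**Precision and coverage.** The visit-specific SE within a subgroup is 8 x √(2/15) = 2.92. Under 7.3 the variance is 4 x 64/60 plus a quarter of the variance of the constant difference, (16/60)/(1'S⁻¹1). For exchangeable 0.4 with equal SDs, 1/(1'S⁻¹1) = 64 x 3/6 = 32. The SE of the difference is then √8.53 = 2.92, and the within-subgroup SE is √(4.27 + 2.13) = 2.53.

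Coverage is Φ(1.96 - b/SE) - Φ(-1.96 - b/SE), with b the bias in absolute value. For the Weeks 8 and 12 pattern, b = 4 - 1.33 = 2.67 and SE = 2.92, which gives 85.0%. Over the first three patterns, 95% intervals for the difference cover 81-93% with equal SDs and 16-76% with rising SDs.

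**Off treatment, if the same terms are used there.** A gap of 4 at off-treatment Days 3 and 7 only is reported at Day 35 as 1.3 to 1.7 with equal SDs, when the truth is 0. The pattern is relevant because the SAP says that "acute effects on eGFR are expected to resolve within 10 to 14 days after stopping treatment".

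**The case against.** **The wording may be shorthand, and the code may be right.** Subgroup-by-treatment can be loose language for a visit-specific contrast, and the programming conventions may list the visit terms. This stands as a limit: the documents show a deficient rule in the SAP, not a wrong analysis that has been run. The unseen document does not repair the text.

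**Pooling over visits is a fair trade in small subgroups.** With about 15 completers per cell this has weight. Under equal SDs the RMSE for a within-subgroup effect is 2.5 to 3.0 under 7.3, against 2.92 for a visit-specific model, so total error is often similar or lower. It does not rescue the intervals, and it weakens if early SDs are smaller: at exchangeable 0.7 with a Weeks 8 and 12 gap, bias 5.45/2 = 2.72 and SE 2.26 give RMSE √(7.4 + 5.1) = 3.5.

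**Stronger readings that the documents do not support.**
- A reader might infer that the difference is known to change on treatment. Protocol 7.3 says "higher bardoxolone methyl doses may be required to have an optimal effect on eGFR following drug withdrawal in patients with macroalbuminuria", but that concerns eGFR after withdrawal and shows no on-treatment time pattern.
- A reader might infer that the primary result is affected. It is not: the subgroup terms are not in that model.
- A reader might infer that the secondary endpoint is affected. Etiology has its own analysis in SAP 7.5.1 and a Week 12 ANCOVA in 7.5.1.1, and no error is shown there.
- A reader might take the off-treatment tables as certainly affected. SAP 7.3 covers those endpoints but cites only the Section 7 model, so this is conditional.

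**Conclusion.** The point holds for the text of 7.3. As written, the Week 12 subgroup difference is a covariance-weighted combination over six visits. It equals the Week 12 value only if the difference is constant or the weights happen to give that value. The existence of the bias, and that it can go either way, follow from the model terms. Its size does not: the ranges rest on assumed correlations, SDs and time patterns, and the equal-SD figures alone are not a full sensitivity range. For a true Week 12 gap of 4 under the rising patterns, the two SD assumptions together give a reported gap from about -1.5 to 2.7. The tables are descriptive with nominal p-values, so this is a cheap improvement and not a threat to the main result.

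**What to change.** In SAP 7.3, state that SUBGROUP x VISIT and SUBGROUP x TRT x VISIT are added to the MMRM, and that the visit-specific treatment contrast is reported within each subgroup. State the same for the off-treatment MMRM. If the programming conventions already contain these terms, copy them into 7.3.

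If the model does not converge, use the visit-specific ANCOVA of 7.4.1.1 or 8.1.1.1 with SUBGROUP and SUBGROUP x TRT. Note there that it drops patients with no value in the window and can be biased if dropout depends on earlier eGFR. For that reason it should be the fallback and not the first choice.

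Keeping the constant term and calling it an average over visits is not enough, because the weights can be negative.

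**Cost.** One sentence. The MMRM gains 10 fixed parameters for a two-level subgroup and 20 for a three-level one, so convergence is less certain. Under equal SDs, within-subgroup intervals become 7-23% wider with complete data (SE 2.92 against 2.37 to 2.73). With 70 patients and 15% missing at Week 12 they become about 8-25% wider with the MMRM and 13-25% with the ANCOVA. If the SD rises from 4 to 8, the SE under 7.3 is 2.21 to 2.30, so the widening is 27-32% (2.92/2.30 to 2.92/2.21).
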